	(Insertion)	
Added the following footnotes:
 
 • ^bSafety Post-Titration visits must be performed 1 month + 1 week after any up-titration in dose and/or frequency in subjects following modified dosing due to Child-Pugh B and Child-Pugh C hepatic impairment. In subjects following the standard dosing regimen, the post-titration visit must be performed only after the first up-titration to 10 mg OCA or matching placebo, or after ≥3 months at a decreased dose or frequency. • ^cPresence or absence of cirrhosis should be assessed per Section 9.7.3. Cirrhosis status should be repeated as clinically indicated. • ^fMayo Risk Score will be calculated based on central laboratory evaluations, diuretic use data, and peripheral edema assessment data captured in the CRF. • ^gChild-Pugh Score will be calculated based on ascites assessment, hepatic encephalopathy grade, and central laboratory evaluations per the Child-Pugh scoring system noted in the eCRF. • ⁿPre-titration tolerability assessment, which include a review of AEs and a review of safety laboratory results (eg, chemistry, hematology, and coagulation), must be completed by the Investigator before any up-titration can occur as defined in Section 7.4.1. Lab results obtained within 2 months prior to any up-titration may be used for assessment. • ^oDose Titration is based on cirrhosis status (Section 9.7.3) and Child-Pugh score (Section 7.3). The initial dose titration of investigational product may occur at the Month 3 visit, or any study visit thereafter for subjects on all dosing regimens, based on tolerability. Subsequent dose titration(s) for 	
Added footnotes provide clarity regarding assessments and visits based on the evaluation of Child-Pugh scores.

--	-------------	--	---

Section	Original Text (Amendment 1.1, 12 November 2015)	Revised Text (Version 3, 07 September 2016)	Justification for Change
		
subjects who are classified as Child-Pugh B or Child-Pugh C and following a modified dosing schedule may occur no earlier than 6 weeks after the previous dose titration. For complete modified dose titration criteria, refer to Appendix A.
 
 • ^PSubjects will be instructed to begin dosing on the day after the Day 0 visit (ie, on Day 1) and to take investigational product at approximately the same time of day. Subjects must be instructed to swallow the tablet whole; they must not chew, divide, or crush the tablet. 	

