7.1.2, Table 2, Schedule of Study Procedures – Year 2 Through End of Study (Table 2 of 2)		
New table- Schedule of Study Procedures – Year 2 Through End of Study (Table 2 of 2)
	
Divided Schedule of Study Procedures into 2 tables, updated to include visits added per updated dosing/titration information.

Section	Original Text (Amendment 1.1, 12 November 2015)	Revised Text (Version 3, 07 September 2016)	Justification for Change
7.3, Planned Dosing Regimen	
7.3 Treatment Assignment Subjects will receive either placebo or 5 mg OCA and should titrate to 10 mg OCA (in a blinded manner) at the 3 month study visit or at any study visit thereafter depending on tolerability.
	
7.3 Planned Dosing Regimen Subjects will be randomized to treatment with either OCA or matching placebo in a 1:1 ratio. Subjects will be dosed according to their cirrhosis status (as defined in Section 9.7.3) and applicable Child-Pugh Score (see Section 9.7.4) as outlined in Table 3.
 
Subjects who are non-cirrhotic or classified as Child-Pugh A at screening will receive 5-mg OCA or matching placebo once daily for 3 months. Subjects should titrate to a maximum dose of 10-mg OCA once daily (or matching placebo) at the Month 3 visit or at any study visit following the Month 3 visit based on tolerability of the product. A review of safety laboratory results (eg, chemistry, hematology, and coagulation) obtained no more than 2 months prior to the planned up-titration visit must be completed as part of the product tolerability assessment before up-titration can occur (see Section 7.4.1).
 
For those subjects that up-titrate to 10 mg, dose may be decreased to 5 mg at any time during the study as considered clinically appropriate (eg, tolerability). Subjects may be titrated back up to a maximum dose of 10 mg once daily based on tolerability and clinical judgment of the Investigator. A review of safety laboratory results obtained within 2 months of the planned up-titration visit date is not required prior to re-challenging a subject up to 10 mg once daily dosing, as long as the decrease in dose/dosing frequency was less than 3 months in duration.
	
Section renamed to reflect changes in titration and dosing for subjects with hepatic impairment.

	(Insertion)	
New: Table 3: Planned Dosing Regimen by Cirrhosis and Child-Pugh Score
 
New: Table 4: Determination of Dosing Regimen
	
Tables added to clarify changes in titration and dosing.

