		
Subjects' dose and dosing frequency may be titrated up or down within the appropriate dosing regimen based on the calculated Child-Pugh Scores. Up-titration should be done per Investigator discretion and be guided by the pre-titration tolerability assessments.
	

Section	Original Text (Amendment 1.1, 12 November 2015)	Revised Text (Version 3, 07 September 2016)	Justification for Change
7.4.1, Pre-Titration Tolerability Assessment Requirements	(Insertion)	
7.4.1 Pre-Titration Assessment Requirements
 
Tolerability of investigational product must be assessed prior to titrating a subject to a higher dose. A review of adverse events and safety laboratory results (eg, chemistry, hematology, and coagulation) obtained within 2 months of the up-titration visit must be performed as part of the investigational product tolerability assessment, prior to any planned up-titration in investigational product (eg, Month 3, Month 6). Safety laboratory results obtained at the Month 1 visit (for titration at Month 3) or at the 1 Month Post-Titration Assessment visit (for titration prior to or at the subsequent quarterly visit) are acceptable for review purposes; however, if for any reason, laboratory results are not available at the time of the planned up-titration visit, additional laboratory samples must be obtained and reviewed, prior to up-titrating the subject to a higher dose.
 
To be eligible for a dose up-titration:
 
 • Subjects should not be experiencing significant AEs that are suspected to be related to investigational product (eg, severe pruritus) or displaying other symptoms that may indicate intolerance of investigational product. • There must be no clinically significant increase (as determined by the investigator) in the subject's liver function tests. Subjects whose total bilirubin is >2× baseline (and >ULN) cannot be up-titrated, and additional unscheduled safety visit procedures, outlined in Section 9.7.19, should be implemented, as required 	Section added to provide guidance for assessing subject tolerability prior to titration.

Section	Original Text (Amendment 1.1, 12 November 2015)	Revised Text (Version 3, 07 September 2016)	Justification for Change

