
Section 7.3 Planned Dosing Regimen, and Table 3
	
Subjects should titrate to a maximum dose of 10 mg OCA once daily (or matching placebo) at the Month 3 visit or at any study visit following the Month 3 visit based on tolerability of the product.
 
Footnotes of Table 3 were re-ordered ^b Planned titration regimen is shown; however, the titration of dose and/or frequency is dependent on subject tolerability and/or changes in cirrhosis status or Child-Pugh score at any time during the study
	
Subjects should titrate to a maximum dose of 10 mg OCA once daily (or matching placebo) at the Month 3 visit or at any study visit following the Month 3 visit based on tolerability of the product and assessment of biochemical response. Up-titration should be considered if ALP and/or total bilirubin are >ULN.
 
^c Planned titration regimen is shown; however, the titration of dose and/or frequency is dependent on subject tolerability, biochemical response, and/or changes in cirrhosis status or Child-Pugh score at any time during the study
	
Rationale 9

Section 7.4 Dose Titration Criteria
	
Insertion
	
Dose titrations may involve increases or decreases in dosing frequency or dose and are dependent on tolerability (as assessed by a review of AEs and safety laboratory results) as well as biochemical response (as assessed by reductions in ALP and/or total bilirubin). In general, down-titration will be done in response to tolerability concerns and can occur at any time while on-study. Up-titration will be done per protocol when subjects have no tolerability concerns and have not achieved an adequate reduction in ALP and/or total bilirubin to within normal limits, or as
	
Added language to clarify titrations (up or down).

Section	Original Text (Amendment 3, 07 September 2016)	Revised Text (Version 4, 10 May 2017)	Justification for Change

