	
Dosing should follow the titration schedule of the new dosing regimen such that the maximum dose within that dosing regimen is ultimately attained, based on tolerability and clinical judgment.
	
assessed by the Investigator, or following resolution of a tolerability concern that previously led to down-titration. Up-titrations may only occur to the maximum dose and frequency for each dosing regimen as defined in Section 7.3.
 
Dosing should follow the titration schedule of the new dosing regimen such that the maximum dose within that dosing regimen is ultimately attained, based on tolerability, biochemical response, and clinical judgment.
 
Changes in Child-Pugh Score that result from a transient, explainable change in laboratory parameters should be documented appropriately and should not necessarily result in a change to the dosing regimen (Appendix A).
	

Section 7.4.1 Pre-Titration Tolerability Assessment Requirements
	
 There must be no clinically significant increase (as determined by the investigator) in the subject’s liver function tests. Subjects whose total bilirubin is >2× baseline (and >ULN) cannot be up-titrated, and additional unscheduled safety visit procedures, outlined in Section 9.7.19 should be implemented, as required. 	
 There must be no clinically significant increase (as determined by the Investigator) in the subject’s liver function tests. 	
Clarification

Section 7.4.2 Safety Criteria for Adjustment or Stopping Doses
	
The text in this section is moved to Section 8.4.
		
To avoid redundancy

Section 7.5 Criteria for Study Termination
	
The window of time for scheduling the visit will be based on a final projection of when the requisite 124 adjudicated events will have been accrued.
	
The window of time for scheduling the visit will be based on a final projection of when the requisite 127 adjudicated events will have been accrued.
	
Rationale 3

Section 8.4
	
[Moved from Section 7.4.2 of Version 3]
		
Clarification

Section	Original Text (Amendment 3, 07 September 2016)	Revised Text (Version 4, 10 May 2017)	Justification for Change

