Table 2, Schedule of Study Procedures Year 2 Through End of Study, footnote a	In subjects following the standard dosing regimen, the post titration visit must be performed only after the first up titration to 10 mg OCA or matching placebo, or after ≥3 months at a decreased dose or frequency. Post-titration visits must be performed 1 month ±1 week after any up-titration in dose and/or frequency in subjects following modified dosing due to Child-Pugh B and Child-Pugh C hepatic impairment.		Post- Titration Visits must be performed 1 month (±1 week) and 2 months (±1 week) after any up-titration in dose and/or frequency in subjects following modified dosing due to Child-Pugh B and Child-Pugh C hepatic impairment. See Appendix A for additional guidance. In subjects following the standard dosing regimen, the Post-Titration visit must only be performed 1 month (±1 week) and 2 months (±1 week) after the first up-titration to 10 mg OCA or matching placebo.		Added to satisfy requirement for monthly visits following any titration, requirement to assess Child-Pugh at every visit.
Table 2, Schedule of Study Procedures Year 2 Through End of Study, footnote e	Mayo Risk Score will be calculated based on central laboratory evaluations, diuretic use data, and peripheral edema assessment data captured in the CRF				MRS score will be calculated by central lab
Table 2, Schedule of Study Procedures Year 2 Through End of Study, footnote g	Height will be collected at this visit				
Table 2, Schedule of Study Procedures Year 2 Through End of Study, footnote j	DEXA will be conducted at 12-month intervals at all study sites where the DEXA device is available				Procedure deleted

Section	Original Text (Amendment 4, 10 May 2017)	Revised Text (Version 5, 04 Jan 2018)	Justification for Change
Table 2, Schedule of Study Procedures Year 2 Through End of Study, footnote m	The subject should be instructed to fast overnight (at least 8 hours) prior to each visit. Fasting is required prior to all study visits (except Screening Visit 1) but water is permitted.	The subject should be instructed to fast overnight (at least 8 hours) prior to each visit. Fasting is required prior to all study visits (except Screening Visit 1) but water is permitted. MELD and MRS values will be calculated based on serum chemistry values at each visit.	MELD and MRS removed as line items. Central lab will calculate these values.

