
Section 7.4, Dose Titration Criteria
	
... Up-titrations may only occur to the maximum dose and frequency for each dosing regimen as defined in Section 7.3.
	
... Up-titrations may only occur to the maximum dose and frequency for each dosing regimen as defined in Section 7.3. A 1-Month and 2 Month Post-Titration Assessment must be performed any time a subject's dose or frequency is up-titrated (see Section 7.1.2 and Section 9.7.7).
	
Clarify dosing assessments.
																																	

Section 7.4, Dose Titration Criteria, Dose Titration due to Change in Cirrhosis or Child-Pugh Score
	
Changes to the dosing regimen are not mandatory and should be based on clinical judgment as well as change in cirrhosis status. provides an overview of the possible changes in dosing regimen due to changes in cirrhosis or Child-Pugh Score.
 
... Changes in Child-Pugh Score that result from a transient, explainable change in laboratory parameters should be documented appropriately
	
... Changes in Child-Pugh Score that result from a transient, explainable change in laboratory parameters should be documented appropriately, and should not necessarily result in a change to the dosing regimen
 
... Changes in Child-Pugh Score that result from a transient, explainable change in laboratory parameters (eg, increase in vitamin K resulting in
	
Clarify that changes in CP scores should be discussed with medical monitor.
																																	

Section	Original Text (Amendment 4, 10 May 2017)	Revised Text (Version 5, 04 Jan 2018)	Justification for Change

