
Section 7.6, Dose Adjustment, Interruption, and Withdrawal from Investigational Product or Study
	
Insertion
	
Investigational product may be temporarily decreased (eg, from 10 mg twice weekly to 5 mg twice weekly, or from 5 mg twice weekly to 5 mg once weekly) or temporarily or permanently stopped based on tolerability concerns. Investigational product may be resumed at the maintenance dose upon resolution of gastroenteritis or worsening renal function or dehydration if there is no evidence of liver injury. For rechallenge following all other dose interruptions (see Table 8), investigational product should be initiated at a lower dose and subjects monitored more frequently with up-titration considered based on tolerability.
 
Adjustments, interruptions, discontinuation, and any rechallenge of investigational product should be implemented per the criteria outlined in Table 8. Subjects that discontinue investigational product are expected to continue in the study (and follow the regular visit schedule) until the end of the study, and the study will terminate at the time when the needed number of adjudicated events has accrued. If a subject reaches an outcome event, he or she should continue the regular visit schedule and continue taking investigational product as long as the subject has not met any of the criteria for mandatory interruption of investigational product outlined in Table 8, and the Investigator assesses it as safe. In general, subjects should be strongly encouraged to both stay on investigational product and remain in the study until study termination.
 
Table 8: Criteria for Dose Adjustment, Interruption, Discontinuation and Rechallenge.
	
Per FDA response, added to provide guidance for monitoring disease progression due to potential hepatic decompensation

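### Section 7.4 and the schedule footnotes disagree on whether 1- and 2-month safety visits follow a return to 10 mg on the standard regimen; a Version 3 waiver of recent labs before that step should be checked in the same edit

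*Protocol*

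**What the plan says.** **After the dose is raised (Version 5).** Section 7.4 states: "A 1-Month and 2 Month Post-Titration Assessment must be performed any time a" subject's dose or frequency goes up, and points to Sections 7.1.2 and 9.7.7. Appendix A repeats the rule. Table 2 footnote a is narrower: "In subjects following the standard dosing regimen, the Post-Titration visit must only be performed 1 month" and 2 months after the first up-titration to 10 mg. Table 1 footnote b has the same limit. Both footnotes, and the visit windows in Section 9.7.1, dropped the former visit after at least 3 months at a reduced dose or frequency. The log justifies these edits by a requirement for monthly visits after any titration.

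**What counts as an up-titration (Version 4).** Section 7.4 makes titration "dependent on tolerability (as assessed by a review of AEs and safety laboratory results) as well as biochemical response", and it includes among up-titrations a step taken "following resolution of a tolerability concern that previously led to down-titration".

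**Before the dose is raised (Version 3).** Section 7.3 says that, for a standard-regimen subject whose reduction lasted less than 3 months, review of safety labs from the previous 2 months "is not required prior to re-challenging a subject up to 10 mg once daily dosing". Schedule footnote n says that the adverse-event and laboratory review "must be completed by the Investigator before any up-titration can occur as defined in Section 7.4.1". Section 7.4.1 says that a review of adverse events and safety results "obtained within 2 months of the up-titration visit must be performed as part of the investigational product tolerability assessment", ahead of any planned up-titration. Neither of these two places mentions an exception.

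**Rechallenge (Version 5).** Section 7.6 adds that "any rechallenge of investigational product should be implemented per the criteria outlined in Table 8"; in Version 6 this is Table 7. The table itself is not in the text available.

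**The concern.** Obeticholic acid carries a known hepatic risk, and Version 5 was written largely to tighten hepatic monitoring. A site that plans visits from the schedule would book no post-titration visit for a subject going back to 10 mg. A site that reads Section 7.4 would book two. The visit in Section 9.7.7 includes adverse-event review, physical examination, chemistry, hematology, coagulation and a Child-Pugh assessment, so the discrepancy decides whether liver tests are looked at soon after the dose goes up. The Version 3 waiver, if it survives, concerns the other side of the same step: whether recent liver tests must be seen before the dose is raised. Nothing here touches sample size, error rates or the primary analysis. It is a matter of safety conduct.

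**Working it through.** The protocol gives no figure to reproduce. The check is a comparison of texts, with simple day counts for size.

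**1. One subject, two rules.** Take a standard-regimen subject on 10 mg, reduced to 5 mg for 10 weeks without interruption, then returned to 10 mg.
- Section 7.4 (Version 4) treats the return as an up-titration, so Section 7.4 (Version 5) requires assessments at 1 and 2 months.
- Table 1 footnote b and Table 2 footnote a (Version 5) require none, because this is not the first step to 10 mg.
- A reduction of 3 months or more earned a 1-month visit under the previous footnotes. Under the Version 5 footnotes it earns none.

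So the footnote edit removed a visit for this case, although its stated purpose was visits after any titration. Both texts are Version 5 revised text, so the comparison is within one version.

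**2. Time to the first scheduled chemistry after the return.** Inputs: quarterly visits, each with a window of 2 weeks either side (Section 9.7.1). Take 1 month as about 30 days, 2 months as 61 and 3 months as 91.
- Return at a quarterly visit, under 7.4: about day 30, then about day 61.
- Same return, under the footnotes: the next quarterly visit, day 91. With both visits at the window extremes, 91 − 28 = 63 to 91 + 28 = 119 days.
- Difference at nominal timing: 91 − 30 = 61 days.

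For a return between quarterly visits, the wait under the footnotes is shorter.

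**3. What the waiver would change, if still in force.** Without it, labs must be no older than 61 days.
- At a scheduled visit, chemistry is drawn the same day. The waiver only decides whether 10 mg is dispensed before or after that result is read. Turnaround time is not given.
- Between scheduled visits, and assuming no unscheduled sample, the last scheduled result is too old for 91 − 61 = 30 days of a quarter. At the window extremes this is 63 − 61 = 2 to 119 − 61 = 58 days.
- Under Close Observation (Section 7.7) liver biochemistry comes every 6 weeks, 42 days, which is inside 61. Monthly post-titration visits, about 30 days apart (37 with the extra week), are inside it too. The waiver has no effect in either setting.

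**4. Who is left.** Close Observation covers interrupted or discontinued drug, and Section 7.6 asks for a lower starting dose and more frequent monitoring when rechallenging after most interruptions. Listed symptoms and laboratory alerts trigger testing (Sections 7.5.1 and 7.5.2). The remaining group is mainly subjects whose dose was reduced without interruption, for instance for pruritus, the main adverse event attributed to the drug and not on the 7.5.1 list. The documents give no count of such re-challenges, so no fraction can be stated.

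**The case against.** The strongest reply on the visits is that Section 7.4 itself points to Section 7.1.2, so the footnotes can be read as the detailed form of a general rule. Appendix A adds little here, because it deals with the modified regimen. That reading is possible, but the sentence in 7.4 is unqualified and the logged reason for the footnotes speaks of any titration. A site cannot tell from the text that the narrower rule is meant.

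The reply on the waiver is stronger. Section 7.3 gives the general rule, cites 7.4.1, and then carves out a narrow case: standard regimen, dose already reached once, short reduction. The 3-month limit matched footnote b of the same version, which points to a deliberate exception. The examples in 7.4.1 are Month 3 and Month 6, and Version 4 Section 7.4 sets no age limit on labs.

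A reader might infer that sites now hold contradictory instructions on labs before re-challenge, or that subjects are returned to 10 mg with no liver tests at all. The documents do not support either. The current body of 7.3 is not shown, the Version 5 entry for its standard-regimen part is an ellipsis, the matching 3-month wording was removed elsewhere in Version 5, and the rechallenge table is not shown.

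Nor should pruritus be read as a hepatic signal. Section 5.7 lists new or worsening pruritus among signs in patients with liver-related events on the marketed drug, but also reports no evidence linking pruritus to stage or progression of disease.

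**Conclusion.** The disagreement between Section 7.4 and the two schedule footnotes holds. On the standard regimen, a return to 10 mg is followed by 1- and 2-month checks under one and by none under the other. For a return at a quarterly visit, that is first scheduled chemistry at about 30 versus about 91 days. This assumes that the Version 5 wording carries into Version 6, whose change log lists no edit to it (minor edits are not logged), and that the unseen rechallenge table does not settle the matter.

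The laboratory waiver is secondary and conditional. It is an unreconciled exception in Version 3, probably intended, and its presence in Version 6 is unverified. If present, it matters mainly for between-visit re-challenge after a reduction without interruption, in roughly the last 30 days of a quarter. Overall priority is low, because routine and symptom-triggered testing already limits the exposure.

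**What to change.** Amend Table 1 footnote b and Table 2 footnote a so that, on the standard regimen, 1- and 2-month post-titration visits follow any up-titration, including a return to 10 mg, as Section 7.4 states. Sites that follow the footnotes would add two short safety visits per re-challenge, which 7.4 already requires. Section 9.7.7 lets the samples be taken locally with a telephone contact where a site visit is not feasible. Narrowing 7.4 instead would also remove the conflict, but it would drop the checks and go against the logged purpose.

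In the same edit, look at the current Section 7.3 and the rechallenge table. If the waiver sentence is still there and the table does not override it, delete it so that 7.4.1 applies: adverse-event review plus labs from within 2 months, drawn and reviewed first if missing. The cost is one sentence and at most one routine blood sample with a short delay per re-challenge.
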